10.0 Procedures Involved

10.1 Provide a description of all research procedures or activities being performed and when they are performed once a subject is screened and determined to be eligible. Provide as much detail as possible.

NOTE: This should serve as a blueprint for your study and include enough detail so that another investigator could pick up your protocol and replicate the research. For studies that have multiple or complex visits or procedures, consider the addition of a schedule of events table in in your response.

Response:

Randomization of subject into one of the three study arms

There will be three arms of this study with each arm testing a different pain reducer: Buzzy Bee, Vapocoolant, and placebo. We will use a sham device e.g. a band around the arm for placebo control.

After obtaining informed consent, the patients will be randomized into one of the three groups following a randomization table created by a statistician. Whichever intervention is randomly selected will be performed on patient prior to the needle stick.

These methods have been used in the ED as part of routine procedures to help patient for pain relief from a needle stick, the RNs are familiar with these methods. However, for the purpose of this study, the training videos will be uploaded in the Kaleidoscope Talent management for RNs to review the procedure and help them to refresh their memories.

Videotaping of subject

Using a camera, an ED research assistant will videotape subject's whole body including the facial expression while phlebotomy and IV catheter placement is performed for scoring of the PBCL. We will tape the entire venipuncture procedure starting from sterilization and ending at the time when the venipuncture is completed. If the first venipuncture procedure attempt is failed, we will not tape the second attempt. This subject will be withdrawn from the study.

Obtaining pain scores from subject and legal guardian using the Faces Pain Scale-Revised instrument

Before and after the venipuncture procedure, we will ask the legal guardian and subject to complete a Faces pain scale revised form. Since the revised form is validated to use for both adult and children, the same document will be used for the legal guardian and children for this study. This document is attached with this submission.

Reviewing of the videotape

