Two physicians will review the video tape independently, and give a score using the PBCL tool. These two physicians are blinded to the study aims. They will be trained on how to use the PBCL by the PI.

In the event when there is a discrepancy of the PBCL score between the two reviewers, the mean of the two scores will be used as the final score.

10.2 Describe what data will be collected.

NOTE: For studies with multiple data collection points or long-term follow up, consider the addition of a schedule or table in your response.

Response:

We will collect demographic data, reason for venipuncture, PBCL score, facial pain score etc.

10.3 List any instruments or measurement tools used to collect data (e.g. questionnaire, interview guide, validated instrument, data collection form).

Include copies of these documents with your submission.

Response:

The following documents will be used for data collection:

1. Data collection form

2. Procedure behavior check list (PBCL)
3. The Faces Pain scale-revised document.

These documents will be submitted with this IRB application.

10.4 Describe any source records that will be used to collect data about subjects (e.g. school records, electronic medical records).

Response:

Kaleida health Electronic power chart records will be used for data collection.

*10.5 Indicate whether or not **individual** subject results, such as results of investigational diagnostic tests, genetic tests, or incidental findings will be shared with subjects or others (e.g., the subject's primary care physician) and if so, describe how these will be shared.*

Response:

No individual subject results will be shared with the subject or others.

*10.6 Indicate whether or not **study** results will be shared with subjects or others, and if so, describe how these will be shared.*

Response:

Study results will not be shared with subjects or others. The final results of this study may be presented at a conference or published in a peer reviewed journal; however, only group data will be publicized in these circumstances, no individual identifiable information will be released.

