14.0 Resources and Qualifications

*14.1 Describe the qualifications (e.g., education, training, experience, expertise, or certifications) of the Principal Investigator **and** staff to perform the research. When applicable describe their knowledge of the local study sites, culture, and society. Provide enough information to convince the IRB that you have qualified staff for the proposed research.*

NOTE: If you specify a person by name, a change to that person will require prior approval by the IRB. If you specify a person by role (e.g., coordinator, research assistant, co-investigator, or pharmacist), a change to that person will not usually require prior approval by the IRB, provided that the person meets the qualifications described to fulfill their roles.

Response:

The study PI [name] is a second year fellow physician in the Emergency Department of Oishei children's Hospital, she is a certified pediatrician. She has participated in clinical researches previously as Co-PI.

[name] and [name] will be the mentors for this project. [name] is an attending physician in general pediatrics department, and [name] is an attending in ED. Both of them have involved in numerous studies as PI and mentors in the past.

The study coordinator has more than 14 years of experience in conducting clinical researches including drug trial, device trial, observational research, double blinded randomized drug trial, chart review study etc. She is familiar with good research practice regulations and rules. She will be responsible for IRB submission and coordinating all study activities for this project.

[name], a pediatric hospitalist, [name] will be the double blinded observers. They will review the tape and give a score based on the PBCL instrument.

The statistician, [name], has extensive expertise in study design and data analysis. He is responsible for study design and data analysis for this study.

Describe other resources available to conduct the research.

A group of research assistants in the ED will be involved in subject recruitment for this study under the supervision of the study coordinator.

14.2 Describe the time and effort that the Principal Investigator and research staff will devote to conducting and completing the research.

NOTE: Examples include the percentage of Full Time Equivalents (FTE), hours per week. The question will elicit whether there are appropriate resources to conduct the research.

Response:

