17.0 Data Management and Analysis

17.1 *Describe the data analysis plan, including any statistical procedures. This section applies to both quantitative and qualitative analysis.*

Response:

All data analyses will be performed with SAS (version 9.2; SAS Institute, Inc., Cary, NC) and R (version 3.0.3) software. Chi-square and Fisher's exact test will be used to compare adverse events (e.g., systemic reaction, anaphylaxis, SOB, dyspnea, excess bleeding or hematoma formation), venipuncture and catheterization first attempt success, and number of patients with no to mild pain during needle insertion.

The Kruskal-Wallis test will be used to compare each of the two observers' assigned scores on the PBCL across three time periods: pre, procedure and post-procedure. Pre-procedure is defined as the time period prior to needle insertion including the placement of Vapocoolant, pain control or sham device up to needle insertion. The procedure period is defined as needle insertion through withdrawal. Post-procedure is defined as the 2 minute time period after needle withdrawal. Only patient and observer pain scores will be used for first-time needle insertion. If first attempt is failed, subject will be withdrawn from the study. Comparisons of pain scores of the five intervention groups to placebo (sham device) will be analyzed via ANOVA.

17.2 If applicable, provide a power analysis.

NOTE: This may not apply to certain types of studies, including chart/records reviews, survey studies, or observational studies. This question is asked to elicit whether the investigator has an adequate sample size to achieve the study objectives and justify a conclusion.

Response:

For chi-square analysis, based on a medium effect size of 0.3, alpha of 0.05, degree of freedom of 8, and 80% power it is estimated we will need a total of 168 subjects (56 per group). (*QFAB Bioinformatics*. 2015)

17.3 Describe any procedures that will be used for quality control of collected data.

Response:

Our RA will double check the data form to assure accuracy and completeness of data collection, if there is any missed data point, the RA will fill in the missing information immediately.

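### The PBCL video reviewers are labelled double blinded, but the only blinding described is to the study aims; blinding to allocation cannot be claimed

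*Combined protocol and SAP*

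**What the plan says.** Section 4.1 describes a single-center, randomized, open-label, placebo-controlled trial. Section 14.1 says that the two video reviewers "will be the double blinded observers". Section 10.1, under review of the videotape, says what they are blinded to: "These two physicians are blinded to the study aims". It adds that they score independently, that the principal investigator trains them on the PBCL, and that the mean is used when their scores differ.

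On the footage, Section 10.1 has a research assistant "videotape subject's whole body including the facial expression while phlebotomy and IV catheter placement is performed for scoring of the PBCL", and sets the window: "We will tape the entire venipuncture procedure starting from sterilization and ending at the time when the venipuncture is completed". The control is described as follows: "We will use a sham device e.g. a band around the arm for placebo control". Section 3.1 describes the Buzzy as a palm-sized vibrating device with ice wings. The third arm is ethyl chloride vapocoolant (Section 31.1).

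Section 17.1, repeated in the Data Management and Analysis text at the end of the document, sets three scoring periods. The first covers the time before the needle goes in, "including the placement of Vapocoolant, pain control or sham device up to needle insertion". Last come the 2 minutes after the needle is withdrawn.

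Section 18.1 A has the coordinator move each video to a secure folder shared with the two physicians. It mentions no cropping, masking or file-naming rule.

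**The concern.** A reader who meets the term double blinded will take it that the observers did not know which intervention each child received. The protocol does not provide for that. It keeps the aims from the observers, which is a different and weaker safeguard, and then gives them footage in which the intervention is likely to be seen.

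This matters because of the role PBCL plays. The hypothesis in Section 1.2 rests on child report, parent report and independent observation. The child and guardian Faces Pain Scale-Revised (FPS-R) ratings come from people who know what was applied. PBCL is the only outcome for which any assessor blinding is claimed. If it is published as double blinded, readers will treat it as blinded confirmation of the open-label ratings, and the design does not support that.

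**Working it through.** **The plan's one computed figure.** Section 17.2 gives 168 subjects for a chi-square test with w = 0.3, 8 degrees of freedom, alpha 0.05 and 80% power. With noncentrality N × w², 80% power needs N = 166.9, so 167, or 168 in three equal arms; power at 168 is 80.3%. The figure reproduces, and the blinding question does not depend on it.

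**What the label needs against what is described.**

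| Question | What the protocol gives |
|---|---|
| What are the observers called? | Double blinded (14.1) |
| Blinded to what? | Study aims (10.1) |
| Blinded to allocation? | Not stated anywhere |
| Trial-level masking? | Open label (4.1) |
| Do the interventions look alike? | No: device with ice wings (3.1), vapocoolant, arm band (10.1) |
| What is filmed? | Whole body, from sterilization to completion (10.1) |
| Is placement part of a scored period? | Yes, the pre-procedure period (17.1) |
| Is the video edited or the arm hidden? | Not described (18.1 A) |

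**Inference on visibility.** If the pre-procedure period is scored from video as 17.1 defines it, the observers watch the intervention being applied. If placement comes before the camera starts, the observers may not see it, but then 17.1 asks them to score something that was not filmed. The same mismatch occurs at the other end: taping stops when venipuncture is completed, while 17.1 scores 2 further minutes after withdrawal. The two sections therefore do not describe the same footage. Whole-body filming may also show a device or band left on during insertion, though the documents do not say whether either stays on.

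**Averaging does not help.** If both observers shift their scores by δ for one arm, the mean of (x₁ + δ) and (x₂ + δ) is (x₁ + x₂)/2 + δ. Averaging reduces random disagreement and leaves a shared shift untouched.

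**Illustration only.** Assume no true effect, 56 per arm, and a shared observer shift of b standard deviations in one arm. For a two-arm comparison at two-sided 0.05 (normal approximation), SE = √(2/56) = 0.189 and the rejection rate is Φ(b/SE − 1.96) + Φ(−b/SE − 1.96). For a three-arm ANOVA the noncentrality is 56 × b² × 2/3, with 2 and 165 degrees of freedom.

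| Assumed shift b (SD) | b/SE | Two-arm rejection | ANOVA noncentrality | ANOVA rejection |
|---|---|---|---|---|
| 0 | 0 | 5% | 0 | 5% |
| 0.1 | 0.53 | 8.3% | 0.37 | 7.9% |
| 0.3 | 1.59 | 35.5% | 3.36 | 35.0% |
| 0.5 | 2.65 | 75.4% | 9.33 | 77.9% |

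The noncentral t gives nearly the same two-arm values (8.2% at 0.1 SD, 74.6% at 0.5 SD). Every value of b is an assumption. The plan names Kruskal-Wallis for PBCL, so these are not operating characteristics of the planned test. The table shows only that a shared shift is not harmless at this sample size.

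**The case against.** The best case for the plan has four parts.

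- **The label is minor.** It appears once, in the staff-qualifications section, and may be loose wording for two independent observers who are kept from the aims. The design and analysis sections do not repeat it. That is fair, but the term has an ordinary meaning, the protocol does not define it otherwise, and it can be carried into a publication.
- **Blinding to aims is real.** It is stated, and nothing contradicts it. A reader might infer that no blinding exists at all; the documents do not support that. Physicians who see three different methods could guess the comparison, but that is conjecture.
- **Visibility is inferred.** A reader might conclude that the observers see the arm in every child. The documents do not go that far: they do not order placement against sterilization, and do not say whether the device or band stays in frame. What stands is that the arm is probably visible in most videos.
- **No bias is shown.** A reader might take the table above as the trial's false-positive rate, in favour of Buzzy. Neither the size nor the direction is in the documents, and raters unaware of the aims need not lean toward Buzzy. This objection stands in full.

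A reader might also conclude that PBCL should be removed from the primary claim. That is debatable: Section 2.1 names anxiety and pain together, and PBCL is the only listed instrument described as rating anxiety (Section 3.1). Nor does any section say that PBCL was chosen to offset the open-label ratings.

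**Conclusion.** The concern holds as a point about what may be claimed. The protocol attaches a double-blind label to observers for whom only blinding to aims is described, in an open-label trial with visibly different interventions and no masking of the video. Blinding to allocation cannot be claimed for PBCL. This rests on two readings: that the label implies allocation blinding in its ordinary sense, and that whole-body footage with a scored placement period will usually reveal the arm.

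The size and direction of any bias are unknown, so the point does not show that PBCL results would be wrong. It limits what they can support: they are an independent observer rating, not a blinded check on the FPS-R. The sample size and the FPS-R analyses are unaffected.

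**What to change.** 1. In Sections 14.1 and 10.1, replace the double-blind label with: *not told the allocation or study aims; allocation may be visible on video*.
2. In Section 18.1 A, require video file names that do not show the arm.
3. Have each observer record a guess of the arm after scoring each video, and report guesses against actual allocation. With three equal arms, chance agreement is one in three. The guess must come after the score so that it does not prompt it.
4. Report PBCL as not blinded to allocation, and do not describe it as blinded confirmation of the FPS-R ratings.
5. Reconcile the taping window in Section 10.1 with the scoring periods in Section 17.1 and its repeat at the end of the document: say whether placement and the 2 minutes after withdrawal are filmed, and score only periods that are.

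The cost is protocol wording, a file-naming rule and one extra item on the observers' form. No subject, visit or assessor is added. The real price is that the claim for PBCL becomes less favourable.

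Trimming the video to the period from insertion to withdrawal is optional. It could hide the placement step, but if the device and band stay on, a child wearing neither would be recognised as the vapocoolant child. The pre-procedure period must also still be scored under the current plan. Trimming is extra work for the coordinator and masks the arm only in part.

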11.0 Study Timelines

11.1 Describe the anticipated duration needed to enroll all study subjects.

Response:

We anticipate completing subject recruitment within 24 months of time.

11.2 Describe the duration of an individual subject's participation in the study. Include length of study visits, and overall study follow-up time.

Response:

The duration of the individual subject's participation in this study will be 5-10 minutes. It will be ended when the patient completes the Facial pain scale sheet. No study follow-up will be done for this project.

11.3 Describe the estimated duration for the investigators to complete this study (i.e. all data is collected and all analyses have been completed).

Response:

The estimated duration for the investigators to complete the study will be 16 months. We will spend 24 months to recruit subject and another 3-4 months for data analysis.

12.0 Setting

12.1 *Describe all facilities/sites where you will be conducting research procedures.*

Include a description of the security and privacy of the facilities (e.g. locked facility, limited access, privacy barriers). Facility, department, and type of room are relevant. Do not abbreviate facility names.

NOTE: Examples of acceptable response may be: "A classroom setting in the Department of Psychology equipped with a computer with relevant survey administration software," "The angiogram suite at Buffalo General Medical Center, a fully accredited tertiary care institution within New York State with badge access," or, "Community Center meeting hall."

Response:

The consenting and videotaping process will be conducted in the private patient room in the ED at John R. Oishei Children's Hospital. Data collection will be completed by our research assistant at their desk in the ED, where the ED is bandage accessed. The video tape will be reviewed at the UBMD Pediatric physician's office located on the ID badge assessed 5th floor of the Conventus building ([name]).

12.2 *For research conducted outside of UB and its affiliates, describe:*

- *Site-specific regulations or customs affecting the research*
- *Local scientific and ethical review structure*

NOTE: This question is referring to UB affiliated research taking place outside UB, i.e. research conducted in the community, school-based research, international research, etc. It is not referring to multi-site research. UB affiliated institutions include Kaleida Health, ECMC, and Roswell Park Cancer Institute.

Response:

N/A: This study is not conducted outside of UB or its affiliates.

13.0 Community-Based Participatory Research

13.1 *Describe involvement of the community in the design and conduct of the research.*

NOTE: Community-Based Participatory Research (CBPR) is a collaborative approach to research that equitably involves all partners in the research process and recognizes the unique strengths that each brings. CBPR begins with a research topic of importance to the community, has the aim of combining knowledge with action and achieving social change to improve health outcomes and eliminate health disparities.

Response:

N/A: This study does not utilize CBPR.

13.2 *Describe the composition and involvement of a community advisory board.*

Response:

N/A: This study does not have a community advisory board.

14.0 Resources and Qualifications

*14.1 Describe the qualifications (e.g., education, training, experience, expertise, or certifications) of the Principal Investigator **and** staff to perform the research. When applicable describe their knowledge of the local study sites, culture, and society. Provide enough information to convince the IRB that you have qualified staff for the proposed research.*

NOTE: If you specify a person by name, a change to that person will require prior approval by the IRB. If you specify a person by role (e.g., coordinator, research assistant, co-investigator, or pharmacist), a change to that person will not usually require prior approval by the IRB, provided that the person meets the qualifications described to fulfill their roles.

Response:

The study PI [name] is a second year fellow physician in the Emergency Department of Oishei children's Hospital, she is a certified pediatrician. She has participated in clinical researches previously as Co-PI.

[name] and [name] will be the mentors for this project. [name] is an attending physician in general pediatrics department, and [name] is an attending in ED. Both of them have involved in numerous studies as PI and mentors in the past.

The study coordinator has more than 14 years of experience in conducting clinical researches including drug trial, device trial, observational research, double blinded randomized drug trial, chart review study etc. She is familiar with good research practice regulations and rules. She will be responsible for IRB submission and coordinating all study activities for this project.

[name], a pediatric hospitalist, [name] will be the double blinded observers. They will review the tape and give a score based on the PBCL instrument.

The statistician, [name], has extensive expertise in study design and data analysis. He is responsible for study design and data analysis for this study.

Describe other resources available to conduct the research.

A group of research assistants in the ED will be involved in subject recruitment for this study under the supervision of the study coordinator.

14.2 Describe the time and effort that the Principal Investigator and research staff will devote to conducting and completing the research.

NOTE: Examples include the percentage of Full Time Equivalents (FTE), hours per week. The question will elicit whether there are appropriate resources to conduct the research.

Response:

The research assistants work 7 days a week, 13 hours per day enrolling patients. The PI will work 1-2 hours per week to address questions related with the study. The two reviewers will work for about 2 hours per week to review the video tape.

14.3 Describe the availability of medical or psychological resources that subjects might need as a result of anticipated consequences of the human research, if applicable.

NOTE: One example includes: on-call availability of a counselor or psychologist for a study that screens subjects for depression.

Response:

This study involves minimum risk to the participant. We will videotape participant's whole body during the needle stick process. We do not anticipate any consequences related with the videotaping procedure.

14.4 Describe your process to ensure that all persons assisting with the research are adequately informed about the protocol, the research procedures, and their duties and functions.

Response:

The PI, mentors and the study coordinator have involved in the development of the study protocol, they are very familiar with the study design and their duties and functions.

The Research assistants will directly work under the supervision of the study coordinator. The RAs' duties will include: screening potential eligible patient, obtaining consent/assent, videotaping patient and legal guardian as well as collecting data on data collection form.

The study coordinator will provide training to all RAs before the RAs start patient's recruitment. The training is focused on the following aspects:

1. Review study protocol by presenting the materials to the RAs with a slide show. The RAs are required to understand the study aims/purpose and the detail of the study procedures.
2. Review data collection forms. The RAs are required to know the inclusion and exclusion criteria for the study and know what kinds of patients are potentially eligible and need to be screened for the study. In addition, they will also be trained on how to collect data on the data collection form.
3. Review the consent documents. The RAs are required to know (a) the contents of the consent documents, (b) how to approach and introduce the study to the legal guardian and patient (c) how to address some of the common questions that the patient may have (d) immediately contact the study coordinator or PI for a question to which they do not know the answer.

The coordinator will ask the RAs to practice the procedures of obtaining consent at the training meeting.

4. The PI will train the study coordinator on how to use the camera to videotape patient. Then the coordinator will train the RAs about this procedure. Practice will be required as part of the training process.

The training log will reflect areas of trainings and demonstrations of competence, including the method used, e.g. role play. The trainer and trainees names will be documented in the training log as one of the regulatory documents.

All our RAs are CITI trained. They have been helping on patient recruitments for a few other studies conducted in the ED and are very familiar with the patient recruitment and consenting procedures.

